8.4.4. Regulatory Reporting Requirements for SAEs

Prompt notification by the investigator to the sponsor of a SAE is essential so that legal obligations and ethical responsibilities toward the safety of participants and the safety of a study intervention under clinical investigation are met. Refer to Section 10.2.4 regarding reporting timelines.

The sponsor has a legal responsibility to notify both the local regulatory authority and other regulatory agencies about the safety of a study intervention under clinical investigation. The sponsor will comply with country-specific regulatory requirements relating to safety reporting to the regulatory authority, Ethics Committees (ECs)/Institutional Review Boards (IRB), and investigators.

Investigator safety reports must be prepared for any SUSARs according to local regulatory requirements and sponsor policy and forwarded to investigators as necessary.

An investigator who receives an investigator safety report describing a SAE or other specific safety information (e.g., summary or listing of SAEs) from the sponsor will review it and will notify the EC/IRB, if appropriate according to local requirements.

8.4.5. Independent Data Monitoring Committee

The IDMC will operate according to a charter. The IDMC structure, participants and other details will be provided in the charter. The charter will be available prior to study start.

The role of the IDMC will be to review unblinded safety data and make recommendations to the sponsor. These recommendations may include continuing the study without modification, continuing the study with modifications, or terminating the study. Additionally, the sponsor will review data on an ongoing basis and may, on discussion with the IDMC, terminate the study if any clinically significant safety signal related to the study intervention is identified. The recommendations of the IDMC, along with the sponsor's decision, will be communicated to the investigators, the ECs/IRBs and the national regulatory authorities as required. The sponsor or its designee agrees to abide by any directives issued by the national regulatory authority or the EC/IRB.

8.5. Genetics

Genetics are not evaluated in this study.

8.6. Biomarkers

To assess the biomarker study endpoints, serum and stool samples will be collected from all infants for biomarker research. All of these samples, or a subset of these samples from a representative cohort of all participants, may be tested to identify analytes of interest.

At Visit 1 Day 1 and Visit 2 Day 28, as indicated in the SoA (Table 2), a blood sample will be collected and processed to serum from all participants. Restricted blood volumes may be dependent on the physician discretion and/or the participant's health/condition. Testing will be determined by the amount of available blood collected.

These serum samples will be tested for biomarkers including, but not limited to, host inflammatory biomarkers and metabolic analysis. No host genetic analyses will be performed.

The maximum amount of blood collected from each participant over the duration of the study will not exceed approximately 4 mL.

Repeat or unscheduled samples may be taken for safety reasons or for technical issues with the samples.

Stool samples for measurement of exploratory biomarkers will also be collected at clinic visits as specified in the SoA (Table 2), in addition to stool samples collected for the secondary endpoint, (refer to Section 9.7.1). Collection will be performed by trained study team staff at specified clinical visits. Either taking temperature or a rectal swab will be performed to stimulate defecation. Defecation at any time during the clinical visit prior to stool collection can substitute for this rectal swab.

Fecal pH and Bristol or similar stool scale will be measured and recorded by the trained study team staff, at the time of stool collection. Samples will be tested for microbiome composition including levels of total Bi-26 measured by nucleotide sequencing and/or polymerase chain reaction. Stool samples may be tested for biomarkers including, but not limited to, inflammatory biomarkers and host and/or bacterial metabolic analysis.

9. Statistical Considerations

9.1. General

All statistical analyses will be performed using SAS® (Version 9.3 or higher).

Analyses of continuous data will be summarized using descriptive statistics where the following parameters will be reported:

- number of observations
- number of missing observations
- mean
- median
- standard deviation (SD)
- minimum (min)
- maximum (max).

Categorical data will be presented with absolute and relative frequency (n and %).

For the summary statistics, the number of decimal places will be the same as for the source data for extreme values (min, max) and will exceed that of the source data by 1 for other parameters. Percentages will be presented with one decimal place and a percent sign (%).

All tests will be two-sided and performed at the two-sided 5% significance level if not otherwise specified. When reporting the results of significance tests p-values will be reported. All confidence intervals will be two-sided at the 95% level, unless otherwise stated.

All data will be presented in subject data listings.

Summary statistics will be presented separately for the treatment and follow-up periods.

9.2. Subject Disposition, Demographics and Baseline Data, Concomitant Medication, and Compliance

9.2.1. Subject Disposition

Number of subjects who were enrolled and randomized, took at least one dose of study supplement, completed the treatment phase, completed the follow-up phase, withdrew including reasons for withdrawal and the number of participants in each analysis set will be summarized. Protocol deviations will be listed.

9.2.2. Demographic and Baseline Data

The demographic, background, characteristics, and baseline data will be presented descriptively. Corresponding summaries will be presented for all participants enrolled.

9.2.3. Concomitant Medication

Medications will be coded by site of action and therapeutic and clinical characteristics using WHO's Anatomical Therapeutic Chemical (ATC) Classification, and will be presented descriptively

9.2.4. Compliance

Compliance will be presented descriptively. Compliance will be used in defining the perprotocol population.

9.3. Randomization

Participants will be randomized in a ratio of 1:1 to each of the 2 treatment arms, Bi-26 or placebo.

A stratification blocking factor will be used in the ratio of 1:2 for $(WAZ \le -3):(-3 \le WAZ \le -2)$ within each treatment arm. Dynamic randomization algorithms will be used to balance treatment arms with respect to the other stratification factor levels (country, age at enrollment (Day 1), discharge destination) and ensure an overall treatment balance.

9.4. Primary Statistical Hypotheses and Sample Size Determination

The primary study hypothesis is that the difference in the mean change from baseline in WAZ is larger for participants randomized to at least 28 days of Bi-26 relative to placebo.

For the sample size calculation for the primary hypothesis, it is assumed that the between_group difference in the WAZ change from baseline is 0.45 with a standard deviation of 1.3. Based on the above assumption(s) using a 2-sided alpha of 5% and a power of at least 90%, a total of 354 participants, 177 in each group, is required.

Assuming a 10% loss to follow-up and a 3% mortality rate, a sufficient number of participants will be screened to ensure approximately 396 randomly assigned participants are enrolled, 198 in each treatment group.

Figure 2: Sample size sensitivity

N/group, 1-sided α =2.5%, Power=90%

9.5. **Populations for Analyses**

For purposes of analysis, the following populations are defined:

- Intention-to-treat (ITT) population: All participants randomly assigned to study intervention.
- **Modified intention-to-treat (mITT) population**: All participants randomly assigned to study intervention, who received at least one dose (including a partial dose) of the study intervention. Participants will be analyzed according to the intervention they were randomized.
- **Per-Protocol (PP) population**: All participants randomly assigned to study intervention, who received the study intervention, have a Day 90 visit, and did not substantially deviate from the protocol procedures. Participants will be analyzed according to the intervention they actually received. Details of criteria for defining the PP population will be specified in the Statistical Analysis Plan (SAP). The inclusion of participants in the PP population will be determined prior to unblinding the study. A participant data listing and a table with protocol deviations will be presented.
- **Safety population**: All participants randomly assigned to study intervention, who received any dose, including a partial dose, of the study intervention. Participants will be analyzed according to the intervention they actually received.

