7.3. Replacement of Participants

Participants prematurely discontinued from the study will not be replaced.

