7.1.3 Justification of Sample Size

[figure not shown]
The primary study hypothesis is that the difference in the mean change from baseline in WAZ is larger for participants randomized to at least 28 days of Bi-26 relative to placebo.

For the sample size calculation for the primary hypothesis, it is assumed that the between group difference in the WAZ change from baseline in 0.45 with a standard deviation of 1.3. Based on the above assumption(s) using a 2-sided alpha of 5% and a power of at least 90%, a total of 354 participants, 177 in each group are required.

Confidential Page 14 of 50

Assuming a 10% loss to follow-up and a 3% mortality rate, a sufficient number of participants will be screened to ensure approximately 396 randomly assigned participants are enrolled, 198 in each treatment group.

Figure 2. Sample size sensitivity

N/group, 1-sided $\alpha = 2.5\%$, Power=90%

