10.3.3 Missing Efficacy data

Missing efficacy data will not be imputed.

Confidential Page 23 of 50

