11 STATISTICAL ANALYSIS METHODS

11.1 Participant Disposition

The following will be presented in a summary table by treatment and overall, for disposition:

- Number of participants screened.
- Number of screen failures.
- Reasons for screen failures.
- Number of participants re-screened.
- Number of participants randomized (ITT population).
- Number of participants randomized but not treated.
- Number of participants who received treatment (Safety population).
- Number of participants who completed the 28-day study intervention period.
- Number of participants who discontinued treatment with reasons.
- Number of participants who completed study up to Day 56 visit.
- Number of participants who withdrew from study prior to Day 56 visit with reasons.
- Number of participants who completed study (up to Day 90 visit).
- Number of participants who withdrew from the study between Days 56 and 90 visits with reasons.

The denominators for the number of participants who completed the 28-day study intervention period and discontinued treatment with reasons will be the obtained from the Safety population. A participant listing for disposition for all participants will be presented including treatment arm, country, study site, date of first and last dose, completed/discontinued treatment with reason and date, completed/withdrew from study with reason and date.

A table summarizing the populations for analysis (including the reasons for exclusion) will be presented by treatment group and overall. A listing will be presented for the ITT population with population excluded from and reasons for exclusion from analysis population for mITT and PP.

A participant listing with randomization information for the ITT population will be provided, including WAZ and age at enrollment (Study Day 1), country, discharge destination date and time of randomization and treatment group. For all participants who are screen failures the following information will be listed: informed consent date, reason for screen failure and eligibility criteria not met.

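### Does randomising 396 infants fail to cover the stated 10% loss to follow-up and 3% mortality?

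*Protocol*

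**What the plan says.** Protocol 9.4 assumes a between-group difference of 0.45 in WAZ change with SD 1.3, two-sided alpha 5%, and "a power of at least 90%, a total of 354 participants, 177 in each group, is required". It then sets the randomised number: "Assuming a 10% loss to follow-up and a 3% mortality rate, a sufficient number of participants will be screened to ensure approximately 396", which is 198 per group. SAP 7.1.3 carries the same requirement ("a power of at least 90%, a total of 354 participants, 177 in each group are required") and the same attrition sentence ("Assuming a 10% loss to follow-up and a 3% mortality rate, a sufficient number of participants"), with no further explanation.

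Three other provisions bear on the point:

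- Protocol 7.3: "Participants prematurely discontinued from the study will not be replaced".
- SAP 10.3.3: "Missing efficacy data will not be imputed".
- SAP 11.1 tabulates two withdrawal periods separately: "Number of participants who withdrew from study prior to Day 56 visit with reasons" and "Number of participants who withdrew from the study between Days 56 and 90 visits with reasons".

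The primary endpoint is at Day 56. A participant completes the study at Day 90 (Protocol 4.4).

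**The concern.** The two rates stand side by side as though both were used to inflate 354, yet the usual ways of applying two separate losses all give more than 396. The base has almost no slack, because 177 per group is the smallest number that reaches 90% power. The inflation step therefore decides whether the stated power survives attrition. Dropouts are not replaced and missing weights are not imputed, so no other provision makes up lost infants. The sentence also gives no time frame, although the SAP itself separates withdrawals before Day 56 from later ones. If the step were simply wrong, the trial would be powered below its stated level at the primary time point, and a reader could not tell what attrition the total protects against.

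**Working it through.** **Inputs.** Difference 0.45, SD 1.3, two-sided alpha 0.05, power at least 90%, 354 evaluable, 10% loss, 3% mortality, about 396 randomised (Protocol 9.4, SAP 7.1.3); 1:1 allocation (Protocol 9.3).

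**Step 1: reproduce the evaluable number.** The normal approximation gives n per group = 2 × [1.3 × (1.960 + 1.282)/0.45]² = 175.4, so 176. With the noncentral t distribution (df = 2n − 2, noncentrality 0.45/(1.3 × √(2/n))), power is 0.8994 at 176 and 0.9011 at 177. The plan's 177 per group, 354 in all, is reproduced exactly.

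**Step 2: inflate 354.**

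| Reading of the two rates | Calculation | Result |
|---|---|---|
| Deaths within the 10% | 354/0.90 | 393.3, so 394 |
| Separate, compounded | 354/(0.90 × 0.97) | 405.5, so 406 |
| Separate, added | 354/0.87 | 406.9, so 407 |
| Simple mark-up, added | 354 × 1.13 | 400.0 |
| Simple mark-up, compounded | 354 × 1.10 × 1.03 | 401.1 |

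The attrition that 396 covers is 1 − 354/396 = 10.6%. It is sufficient on the first row. Against 406 and 407 it is 10 and 11 short, or 2.5% and 2.8% of 396.

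**Step 3: evaluable infants and power at 396** (noncentral t, unadjusted, counting every infant without a Day 56 weight as contributing nothing).

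- Deaths within the 10%: 396 × 0.90 = 356.4 evaluable, power 90.3%.
- Compounded, all before Day 56: 396 × 0.90 × 0.97 = 345.7 evaluable, power 89.4%.
- Added, all before Day 56: 396 × 0.87 = 344.5 evaluable, power 89.3%.

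The largest shortfall is 90 − 89.3 = 0.7 percentage points.

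**Step 4: rates read as whole-study (Day 90) figures.** To keep 354 at Day 56, the share of losses that may fall by then is 10.6/13 = about 82% if the rates add, and 10.6/12.7 = about 84% if they compound. If losses were spread evenly from Day 1 (an assumption), 55/89 = 62% would fall by Day 56, leaving 396 × (1 − 0.13 × 0.62) = about 364. Losses could cluster soon after discharge, and the documents do not settle this.

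**Step 5: what the planned model would need to add.** SAP 11.5.2.1 adjusts for baseline WAZ, age, country and discharge destination. If covariates explain a fraction R² of the outcome variance, the effective number per group is n/(1 − R²). Reaching 90% power needs about 176.4 per group:

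- 172/(1 − 0.025) = 176.4
- 173/(1 − 0.019) = 176.4

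So an R² of about 2% closes the gap on the worst reading. The documents give no correlations, so this gain is plausible but not established.

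**The case for a change.** The best argument for a change is that rounding does not explain the gap. Taken as a separate loss, the 3% mortality adds about 12 infants (406 against 394 for the 10% alone), and 396 falls 10 short of 406. On that reading nearly the whole allowance for deaths is missing. The even split of 198 per group looks like a calculated target, not a loose round number. A mortality rate without a period is also hard to interpret, since the protocol's own introduction cites post-discharge mortality over both three months and one year.

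What stands is that both documents are silent on how the rates combine and over what period, and that 396 covers 10.6% and no more. What does not stand is the step from there to an error. Counting deaths as part of the loss to the primary endpoint is an ordinary reading, and 396 meets it. There is even a route to exactly 396 from the plan's own figures: 177/0.90 = 196.7, so 197 per arm, and the next number divisible by three is 198, which suits the 1:2 WAZ ratio in Protocol 9.3 (66 + 132). The documents do not state that derivation, so it is only a conjecture, but it shows that 396 need not be a mistake.

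The rules on non-replacement and non-imputation add little. The first is why a sample size is inflated at all. The second does not restrict the primary analysis to infants weighed at Day 56, because the repeated-measures model also uses Day 28 and Day 90, so an infant lost after Day 28 still contributes.

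**Conclusion.** No change to the plan is called for. The 354 is right. The approximate 396 is adequate if deaths fall within the 10%, and it can also be adequate if the rates describe the whole study to Day 90. It falls short only if the rates are separate and more than about 82 to 84% of the losses come before Day 56. At worst, with all of them before Day 56, about 345 infants are evaluable and unadjusted power is 89.3 to 89.4%, at most 0.7 points under the target. This rests on the plan's own difference and SD and on a two-sample calculation that gives no credit for covariates or for the Day 28 and Day 90 weights.

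What remains is missing detail. A clause saying whether deaths sit within the 10%, and by which day, would help a reader. It would leave 396 in place and would not affect how the trial is run, analysed or interpreted.

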9.6. Statistical Analyses

The principal features of the statistical analysis are described in this section. A more technical and detailed document of the features will be found in a separate SAP, which is to be finalized before unblinding of the study. When the study is completed and the data are collected, a blinded review of the planned analysis will be carried out. The review will look at the definition of outliers, violators, and exclusion of participants or data from the analysis sets. Decisions made based on the review will be documented.

9.7. Primary and Secondary Estimands

Participants randomized to the group receiving 28 days of Bi-26 will be compared to participants randomized to 28 days of placebo for the primary analysis.

Following International Council for Harmonization of Technical Requirements for Pharmaceuticals for Human Use (ICH) E9 (R1) addendum, the estimands relating to the study objectives are constructed by using the 5 following attributes:

- (a) treatment
- (b) population
- (c) variable/endpoint
- (d) population level summary
- (e) intercurrent events.

These attributes were specified to translate the study objective(s) into a treatment effect that is to be estimated (estimand). Refer to Table 4 and Table 5 for a summary of the primary and secondary estimands, respectively.

| Objective | Primary Estimand |
|---------------------------|-------------------------------------------------------------------------------------------------------------------------------------------------------------------------------------|
| To evaluate the change in | a. Population : The mITT population will be used for the analysis. |
| age) of infants receiving | b. Endpoint : WAZ change from baseline (Day 1) to the Day 56 visit in Bi-26 group. |
| B1-20 | c. Population level summary : Mean change from baseline in WAZ in the Bi-26 group compared to placebo with stratification blocking factors and feeding regimen covariate(s). |
| | d. Intercurrent event(s) : Including but not limited to treatment discontinuation. Further details will be specified in the SAP . |

Table 4: Primary Estimands

| Objective | Secondary Estimand | | | | |
|--------------------------------------------------|-------------------------------------------------------------------------------------------------------------------------------------------------------------------------------------------------------|--|--|--|--|
| To evaluate the change in | a. Population : The mITT population will be used for this analysis. | | | | |
| weight of infants receiving Bi-26 | b. Endpoint : weight change (in grams) from baseline (Day 1) to the Day 56 visit in Bi-26 group. | | | | |
| | c. Population level summary : Mean change from baseline in weight in the Bi-26 group compared to placebo with stratification blocking factors and feeding regimen covariate(s). | | | | |
| | d. Intercurrent event(s): Including but not limited to treatment discontinuation. Details will be provided in the SAP. | | | | |
| To estimate the treatment | e. Population : The PP population will be used for the analysis. | | | | |
| response over time associated with Bi-26 | f. Endpoint : WAZ change from baseline (Day 1) over time through the Day 90 visit (longitudinal assessment) by duration of dosing. | | | | |
| | g. Population level summary : Mean change from baseline in WAZ over time in the Bi-26 group compared to placebo with stratification blocking factors and feeding regimen covariate(s). | | | | |
| | h. Intercurrent event(s) : Including but not limited to treatment discontinuation. Details will be provided in the SAP. | | | | |
| To assess the proportion | a. Population : The PP population will be used for the analysis. | | | | |
| of infants who achieve a specified change in WAZ | b. Endpoint: Proportion of infants with a ≥ 0.3, 0.4, and 0.5 change in WAZ from baseline (Day 1) to Day 56 visit. | | | | |
| from baseline to Day 56 | c. Population level summary : Frequency and percentages of infants with a $\geq 0.3, \geq 0.4$, and ≥ 0.5 change in WAZ from baseline (Day 1) to Day 56 in the Bi-26 and placebo groups. | | | | |
| | d. Intercurrent event(s) : Including but not limited to treatment discontinuation. Details will be provided in the SAP. | | | | |
| To assess the proportion | a. Population : The PP population will be used for the analysis. | | | | |
| of infants who achieve a | b. Endpoint : Proportion of infants with a WAZ >-2 at Day 56 visit. | | | | |
| specified WAZ at Day 56 | c. Population level summary : Frequency and percentages of infants with a WAZ >-2 at Day 56 in the Bi-26 and placebo groups. | | | | |
| | d. Intercurrent event(s): Including but not limited to treatment discontinuation. Details will be provided in the SAP. | | | | |
| To assess the re- | a. Population : The PP population will be used for the analysis. | | | | |
| hospitalization rate | b. Endpoint : Number of re-hospitalizations for acute non-surgical illness through the Day 56 visit. | | | | |
| | c. Population level summary : Frequency (and percentages) of re- hospitalizations in the Bi-26 group compared to placebo. | | | | |
| | d. Intercurrent event(s) : Including but not limited to treatment discontinuation. Details will be provided in the SAP. | | | | |

Table 5: Secondary Estimands

